3 INVESTIGATIONAL PLAN

This is a multi-center, uncontrolled observational study of patients who at the time of entry were prescribed with HUMIRA®(adalimumab) following normal clinical practice, with or without other anti-rheumatic treatments, prior to enrollment in this study.

Patients will be followed for 5 years within the post-marketing observational study.

Physicians will be provided with a study kit that includes a protocol, patient informed consent forms, adverse event report forms, and Data Report Forms (DRFs), for each patient to be enrolled. The participating physician will already have provided a prescription to the patient for HUMIRA®(adalimumab), along with instructions for appropriate use according to the European Union (EU) Summary of Product Characteristics (SPC).

Once the physician has determined that the patient meets the inclusion criteria, and the patient has agreed to be included in the observational study, the patient's baseline demographic data, and disease status will be reported in the Baseline DRF. The physician will then follow-up the patient via regular office visits at intervals as determined by routine clinical practice or as recommended by national guidelines.

Patient's safety and efficacy data if they are part of clinical routine will be recorded in the DRFs at Baseline, and regular visits which are closest to Month 3, Month 6, Month 9, Month 12, Month 18, Month 24, Month 30, Month 36, Month 42, Month 48, Month 54, and Month 60. While the physician will likely deem it appropriate and necessary to have the patient return for intermediate visits during the study period, data will be collected via DRFs only at the intervals which correspond closely to those described above. Physicians are encouraged to treat their patients as they would in their routine clinical practice. If treatment with HUMIRA®(adalimumab) is permanently discontinued for any reason, patients will be discontinued from the study and the reason should be recorded. Physicians will be asked to record adverse events up to 3 months after last administration of HUMIRA®(adalimumab) on the DRF of the next scheduled data collection time.

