3.3.6 Primary Data Collection

The following safety information will be collected: adverse events and serious adverse events. The description of event, start and end date, severity, outcome, causal relationship, and action taken will be recorded.

Data to allow determination of patient's disease activity will be collected. These are 28 joint count of swelling and tenderness (SJC, TJC), physician's global assessment of disease activity, HAQ, ESR and CRP. These data, if available as a result of usual medical practice, will be collected via the DRFs.

Other Data

Changes in concomitant DMARDs, steroids, and NSAIDs as well as the administration schedule of HUMIRA® (adalimumab) should be documented in the DRFs.

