1.5 Derived Data

- Study duration (year) = (visit date of last visit – visit date of baseline visit)/365.25

- Completed patients: patients with ≥ 1734 days study duration

- Treatment duration (year):

For completed patients:

(Date of last visit – Date of baseline visit)/365.25

For not completed patients:

Sum of number of weeks/52, months/12 and years patient has been on drug documented on the last visit

If missing: (Date of last visit – Date of baseline visit)/365.25

Note: Some patients stopped Humira temporally. The periods of not taken Humira are not taken into account for the analysis. These patients will be considered as having taken Humira during the complete study.

- Treatment duration category:

0 to 3 months

> 3 to 6 months

> 6 to 9 months

> 9 to 12 months

> 12 to 18 months

> 18 to 24 months

> 24 to 30 months

> 30 to 36 months

> 36 to 42 months

> 42 to 48 months

> 48 to 54 months

> 54 to 60 months

> 60 months

- For the purpose of the analysis of the evolution of parameters over time, follow-up visits will be classified into time windows, defined upon the number of days between Visit 1 and the date of each subsequent visit (PERIOD = Date of follow-up visit - Date of Visit 1)

- Period = Date of visit – Date of baseline visit

- Month 3 window: $1 \leq \text{period} \leq 137$ days

- Month 6 window: $138 \leq \text{period} \leq 228$ days

- Month 9 window: $229 \leq \text{period} \leq 319$ days

- Month 12 window: $320 \leq \text{period} \leq 456$ days

- Month 18 window: $457 \leq \text{period} \leq 639$ days

- Month 24 window: $640 \leq \text{period} \leq 821$ days

- Month 30 window: $822 \leq \text{period} \leq 1004$ days

- Month 36 window: 1005 <= period <= 1186 days
- Month 42 window: 1187 <= period <= 1368 days
- Month 48 window: 1369 <= period <= 1551 days
- Month 54 window: 1552 <= period <= 1733 days
- Month 60 window: 1734 <= period <= 1916 days

Each visit will be classified in a time window. If the date of the visit is completely missing, it will be assumed that the visit took place on the target day of the window as indicated on top of the follow-up page. If more than one follow-up visit is classified into the same time window, the visit closest to the target day is retained. If within a time window there are two visits at the same distance from the target day, the visit which comes first (e.g. before the target date) is retained. If there are two visits on the same date, the first record is retained.

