2 STATISTICAL ANALYSIS

The analysis of the baseline data and prior anti-TNF treatment will be performed broken down by indication (RA, PsA, AS). Within each indication, baseline data will also be presented broken down by completed/not completed patients. Statistical tests will be performed to compare baseline data for patients completed/not completed the study.

The analysis of treatment duration and the evolution of different parameters over time, will be performed broken down by indication (RA, PsA, AS).

The analysis of adverse events will be performed for all patients together and broken down by indication (RA, PsA, AS):

- Overall
- Per year (up to 5 years)
- By cumulative yearly period (till 5 years)
- Incidence
- Incidence divided by total exposure to treatment (till 5 years).
- Reason for seriousness
- Serious adverse events: number of patients and incidence by system organ class and preferred term
- Non-serious adverse events: number of patients by system organ class and preferred term

If an adverse event has no onset date, the observation date will be taken as onset date. Events that are coded with multiple MedDRA Terms will be counted as separate event.

The percentages in the adverse event table are calculated as follows:

Table	Nominator	Denominator
Number of patients with an adverse event per year.	Number of patients treated in that year with at least one adverse event in that year.	Number of patients treated in that year.
Number of patients with an adverse event per cumulative year	Number of patients with at least one adverse event in that year or before.	Number of patients.
Number of adverse events by total exposure to treatment	Number of adverse events in that year or before.	The sum of the patients' treatment exposure time in that year or before.

The following tables will be presented:

Rheumatoid Arthritis

- 1 Baseline Characteristics– All Patients and Broken Down by Early Termination**
 - 1.1 Age
 - 1.2 Gender
 - 1.3 Disease Duration Before Inclusion
 - 1.4 Anti-TNF use Before Inclusion
 - 1.4.1 Anti-TNF Naïve / Experienced
 - 1.4.2 Types of Anti-TNF use Before Inclusion
 - 1.5 Physician's Assessment of Disease Activity
 - 1.6 Clinical Examination
 - 1.6.1 Joint Assessment (tender joints count, swollen joints count)
 - 1.6.2 Inflammatory Parameters (CRP, ESR)
 - 1.6.3 Physical Function (HAQ %)
 - 1.7 Concomitant Medication
 - 1.7.1 Concomitant Steroids
 - 1.7.2 Concomitant NSAIDs
 - 1.7.3 Concomitant Immunomodulators

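### SAP 1.5 does not define treatment exposure consistently: treatment duration is overstated for completers with a stop, and the exposure-based adverse event rates mix observation time with on-drug time

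*SAP*

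**What the plan says.** SAP 1.5 (Derived Data) sets the threshold first: "Completed patients: patients with ≥ 1734 days study duration", which is 1734/365.25 = 4.75 years. Treatment duration is then derived by one of three routes:

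- Completers: date of last visit minus date of baseline visit, in years.
- Non-completers: "Sum of number of weeks/52, months/12 and years patient has been on drug documented on the last visit".
- Non-completers whose record is missing: the same calendar formula as completers.

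A Note follows: "Note: Some patients stopped Humira temporally". It continues: "The periods of not taken Humira are not taken into account for the analysis". Read alone, that second sentence could mean that gap time is left out. The third settles the matter: "These patients will be considered as having taken Humira during the complete study". The Note is not limited to completers.

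In SAP section 2, the denominator of the exposure-based event table is the sum of the patients' "treatment exposure time in that year or before". The numerator is every adverse event up to that point, with no restriction to time on drug. Section 2 does not define exposure time. Treatment duration in 1.5 is the only candidate definition in the SAP, and I take it to be the one meant.

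Under Protocol section 3, only permanent discontinuation takes a patient out of the study, and no limit on a temporary stop is stated. The same section says: "Physicians will be asked to record adverse events up to 3 months after last administration of HUMIRA®(adalimumab". Protocol section 4 has the investigator monitor adverse events for as long as the study lasts. Protocol 3.3.6 says that "the administration schedule of HUMIRA® (adalimumab) should be documented in the DRFs".

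**The concern.** A quantity called treatment duration, and a rate called incidence per exposure to treatment, should rest on one definition of being treated. Here the SAP acknowledges that some patients were off drug for a time and counts that time as treatment, while using a record of time on drug for another group. Two programmers could derive different values for the same non-completer and each could cite SAP 1.5.

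Two sets of output are affected. Tables 2.1.1 to 2.1.4, for each indication, describe how long patients were treated, which is part of the protocol's long-term use objective. Tables 3.5.1 to 3.5.3, for each indication and for all patients, are the exposure-adjusted safety results in a study whose introduction puts safety at its centre.

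**Working it through.** **1. The routes side by side**

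| Patient | Formula in SAP 1.5 | What the Note does if there was a stop |
|---|---|---|
| Completer | Calendar time | Agrees: the stop is already inside the formula |
| Non-completer, on-drug time documented | Documented time | Conflicts if the record is net of stops: the formula leaves the stop out, the Note puts it in |
| Non-completer, record missing | Calendar time | Agrees: the stop is inside the formula |

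The documents do not say whether the documented time is net of stops or elapsed time since the start of treatment. Nor do they say whether it begins at baseline. Patients are already on drug at entry (Protocol 3.1.1), so it might include time before baseline, which the calendar formula excludes.

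**2. No stated figure to reproduce.** The documents give no person-years, no event rate, no number of patients with a stop and no length of stop. What follows is a range under assumptions.

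**3. Size of the overstatement for completers.** Let p be the share of completers with a stop, g the mean stop in months, and 60 months the follow-up. The off-drug share of calculated exposure is f = p × g / 60, and exposure is overstated by f / (1 − f).

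| p (assumed) | g (assumed) | f | Exposure overstated by |
|---|---|---|---|
| 5% | 1 month | 0.05 × 1/60 = 0.08% | 0.08% |
| 10% | 3 months | 0.10 × 3/60 = 0.5% | 0.5% |
| 20% | 6 months | 0.20 × 6/60 = 2.0% | 2.0% |
| 40% | 12 months | 0.40 × 12/60 = 8.0% | 0.08/0.92 = 8.7% |

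For all patients pooled, assume that completers supply 50% to 90% of person-time and that non-completers add no off-drug time. The off-drug share is then 0.25% to 0.45% in the second row, 1.0% to 1.8% in the third and 4.0% to 7.2% in the fourth.

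**4. Direction of the rate for patients with stops.** If only the denominator is corrected, the reported rate is (1 − f) times the corrected one. But the numerator also holds events that began during stops. Compare instead with a rate that uses on-drug events and on-drug time, and let r be the off-drug event rate divided by the on-drug rate. Then reported/on-drug = (1 − f) + f × r.

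| f | r = 0 | r = 0.5 | r = 1 | r = 1.5 |
|---|---|---|---|---|
| 2% | 0.98 | 0.99 | 1.00 | 1.01 |
| 8% | 0.92 | 0.96 | 1.00 | 1.04 |

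The reported rate is too low only if r is below 1. One assumed patient shows both directions: 5 years, a 6-month stop, 5 events.

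- SAP method: 5/5.0 = 100 per 100 patient-years.
- Gap removed from the denominator only: 5/4.5 = 111.1.
- Gap removed and one off-drug event removed as well: 4/4.5 = 88.9.

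**5. An opposite mismatch in non-completers.** Events up to 3 months (0.25 year) after the last dose can be counted, while documented on-drug time, if it ends at the last dose, has no matching person-time. With a constant event rate and full capture over those 3 months, the rate is inflated by the factor (t + 0.25)/t, where t is years on drug. That is 1.25 at t = 1 and 2.25/2 = 1.125 at t = 2. These are upper figures under those assumptions.

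**The case against.** The best defence is that an observational study may properly use all follow-up time, that the Note applies one rule to everyone who stopped, and that events during stops are counted along with the time. On that view the rate is a coherent rate per year of observation. The study is also uncontrolled and the protocol plans no inferential statistics, so a shift of a few percent changes no stated decision.

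Much of this stands. It limits the point in three places where a reader might infer more:

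- **That adverse event rates are understated.** Steps 4 and 5 show that the sign depends on the off-drug event rate and on post-dose events in non-completers. Nor does the 3-month collection rule show that events late in a long stop go unrecorded. It directly follows the text on permanent discontinuation, and Protocol section 4 has patients monitored throughout.
- **That completers are credited with gaps and non-completers are not, with a jump in exposure at 1734 days.** The Note covers all who stopped temporarily. Such a jump would appear for a temporary stop only if the Note were ignored. What the text supports is an unresolved conflict between the Note and the documented-time formula.
- **That subtracting stops is a simple programming change.** The SAP shows that stops occurred, and the protocol asks for the administration schedule, but neither shows that stop and restart dates exist. Forms are completed only every 3 to 6 months, and SAP 1.2 reports that the database already needed hardcoded corrections.

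The defence does not remove the defect. Observation time is a legitimate denominator, but the SAP does not use it for everyone: non-completers without a stop still get documented on-drug time. It also labels the result as exposure to treatment. Either the formula or the label has to change.

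**Conclusion.** The point holds as a matter of inconsistent definition. Treatment duration in tables 2.1.x is overstated for any completer with a stop; that follows directly from the SAP's own rule and involves no numerator. Tables 3.5.x combine observation time and on-drug time under a treatment-exposure label. The direction of the resulting rate bias is not determined.

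The size is unknown. The illustrative range is about 0.1% to 8% of completers' calculated exposure, and the upper end needs 40% of completers to have stopped for a year on average. The conclusion for tables 3.5.x also rests on reading exposure time in section 2 as treatment duration in 1.5, which is an inference. The point deserves correction because the SAP states the rule outright and the remedy is small. It does not show that the safety results are materially wrong.

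**What to change.** Define exposure once in SAP 1.5, derive it the same way for completers and non-completers, refer to that definition in section 2, and match the numerator to it. Two versions would serve:

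- **(a) On-drug time.** Subtract documented stops for every patient. For tables 3.5.x, apply the same post-administration window, for example the protocol's 3 months, to both events and person-time. Stops shorter than the window then stay in the denominator, so the change in the rates could go either way.
- **(b) Observation time.** If stop and restart dates are too incomplete, use calendar time for everyone, count events over that same time, and label the rate per patient-year of observation. Tables 2.1.x should then say that interruptions are included.

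In either case, reconcile the Note with the non-completer formula, and state whether the documented on-drug time is net of stops and whether it starts at baseline. Report the number of patients interrupted and the documented time off drug, and show the version not chosen as a sensitivity analysis.

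The cost is a SAP text change, a revised derived variable and a rerun of tables 2.1.x and 3.5.x. Version (a) also needs a rule for incomplete gap dates, and how well it works depends on what the forms contain. This concerns analysis only; no change to treatment is proposed.

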3.2.2 Efficacy Variables

Data on the following individual parameters will be collected if assessed as part of clinical practice at each site:

- 28 joint assessment

- physical function (HAQ)
- inflammatory parameter (ESR, CRP)
- concomitant medication
- change in concomitant steroids, NSAIDs
- assessment of non-medical complications (number of non-working days, number of days of hospitalization, ...)
 - for patients with polyarticular or oligoarticular erosive psoriatic arthritis:
 - % of the Body Surface Area (BSA) with psoriatic skin lesions
 - for patients with oligoarticular erosive psoriatic arthritis:
 - Numerical Rating Scale (score of 0 to 10) for the disease activity in the most important joint by the patient (0 = no disease activity during the previous days, 10 = maximal activity during the previous days)
 - Numerical Rating Scale (score of 0 to 10) for the disease activity in the most important joint by the physician (0 = no disease activity during the previous days, 10 = maximal activity during the previous days)
 - For patients with Ankylosing spondylitis the BASDAI will be measured

Table 1: Schedule of Study Assessments

Procedure	Day 1	Month* 3, 6, 9, 12, 18, 24, 30, 36, 42, 48, 54, 60
Informed Consent	✓	
Demographics	✓	
Safety Data Collection	✓	✓
Efficacy Data Collection	✓	✓
Concomitant DMARDs, steroids, NSAIDs	✓	
Changes in concomitant DMARDs, steroids, NSAIDs		✓
Data Report Form Completion	✓	✓

* Data collection at regular visits which are closest to time points described

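### The time-window rule keeps one whole visit without checking that the analysed parameter was recorded, so a value measured at another visit in the same window can be dropped

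*SAP*

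**What the plan says.** SAP 1.5 (Derived Data) sets up the windows and their purpose: "For the purpose of the analysis of the evolution of parameters over time, follow-up visits will be classified into time windows". The windows are contiguous, from day 1 to day 1916, and are 91 to 183 days wide. The unit placed in a window is the visit.

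Three rules then choose one visit:

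- Several visits in a window: "the visit closest to the target day is retained".
- Two visits equally far from the target day: "the visit which comes first (e.g. before the target date) is retained".
- Two visits on one date: "If there are two visits on the same date, the first record is retained".

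For a visit whose date is completely missing, "it will be assumed that the visit took place on the target day of the window", the window being the one printed on the follow-up page.

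On what a visit contains, Protocol 3.2.2 says: "Data on the following individual parameters will be collected if assessed as part of clinical practice at each site". Protocol 3.3.6 puts the same condition on joint counts, physician's global assessment, HAQ, ESR and CRP. SAP 1.2 adds that DAS28 was entered only from 2010.

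**The concern.** Windows are needed because visit timing follows routine practice, and blanks are expected because measurement does too. The selection rule deals with timing and ignores blanks. If the retained visit has no HAQ and another visit in the same window has one, the patient contributes no HAQ to that window, although it was measured within limits the SAP accepts.

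At stake is the number of values behind the follow-up efficacy tables in SAP section 2: every parameter shown in each window, every difference from baseline, the HAQ reduction counts and BASDAI responder status. Table 2.1.4 (treatment duration by DAS28 category at Month 6) is also exposed. A patient whose retained Month 6 visit lacks DAS28 has no category there, even if another Month 6 visit recorded one.

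A second feature of the same rule is that an undated visit sits at distance zero from the target, so an assumed date usually outranks an observed one.

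**Working it through.** The plan gives no count of multi-visit windows, undated visits or missing parameters, so there is no figure to reproduce. The check has four parts.

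**1. Can the rule drop a measured value?** The Month 6 window is days 138 to 228. The SAP does not give target days as day numbers, so I assume months × 365.25/12. This is consistent with the plan: midpoints between successive targets fall within 2 days of every printed upper bound. For Month 6 the target is 6 × 365.25/12 = 182.6, rounded to 183. Take visits on days 140 and 225. Their distances are |140 − 183| = 43 and |225 − 183| = 42, so day 225 is retained. If HAQ was recorded on day 140 only, it is lost. Had day 140 been the only visit in the window, its HAQ would have been used.

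**2. How much could be regained?** Let d be the share of occupied patient-windows (at least one visit) that hold two visits, and q the chance that a visit records the parameter. Neither is in the documents.

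- Chance of a value under the SAP rule: q.
- Chance of a value in a two-visit window with per-parameter selection and independent recording: 1 − (1 − q)².
- Absolute gain over all occupied windows: d × [1 − (1 − q)² − q] = d·q(1 − q).
- Relative gain: d·q(1 − q)/q = d(1 − q).

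| Assumed d | Assumed q | Relative gain d(1 − q) | Absolute gain d·q(1 − q) |
|---|---|---|---|
| 5% | 0.8 | 1% | 0.8 points |
| 5% | 0.6 | 2% | 1.2 points |
| 20% | 0.8 | 4% | 3.2 points |
| 20% | 0.6 | 8% | 4.8 points |

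If recording at two visits of the same patient has correlation r, the relative gain becomes d(1 − q)(1 − r). For assumed r of 0.5 to 0.9, the range runs from 1% × 0.1 = 0.1% to 8% × 0.5 = 4%. With r = 1, meaning a site always or never measures the parameter, it is zero.

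**3. Do the record counts in SAP 1.2 give d?** No. Non-baseline records number 47378 − 5947 = 41431. Per patient this is 41431/5920 = 7.0, against 12 windows, or 41431/71040 = 58% of the 12 × 5920 possible patient-windows. The records are counted before cleaning and the patients after it. The records may also include the LT visits that SAP 1.4 excludes. An average below one per window does not show how often two visits share a window.

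**4. How often does an undated visit displace a dated one?** With the same assumed targets, rounded to whole days, I compared an undated visit with one dated visit on each day of each window. The undated visit is strictly closer on every day except the target day, that is on 1916 − 12 = 1904 of 1916 days (99.4%). On the 12 target days both have distance zero and the same date, so record order decides. The 99.4% counts calendar positions. It is not a probability, since real visits may cluster near the target. The rule covers only completely missing dates. SAP 1.5 does not say how partial dates are handled.

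**The case against.** The strongest objection is that the effect may be negligible. Protocol 3 restricts data collection to visits near the scheduled months, and Protocol 3.3.7 accepts the visit that best matches each time point, so the design intends one form per time point. SAP 1.2 says cleaning resolved duplicate patients and misclassified visits, which would remove some shared windows. Recording tied to each site's practice makes blanks at two visits of one patient likely to coincide, and before 2010 both would lack DAS28. Follow-up efficacy is descriptive, and no direction of bias follows. All of this stands, and it limits the size. It does not remove the gap: the SAP itself foresees several visits in a window and then ignores completeness.

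Whole-visit selection also has a merit, in that all parameters in a window come from one day and one form. That is a real cost of the change, but a modest one, because the tables summarise each parameter separately.

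SAP 1.4 defers data-handling rules to the Statistical Report. A per-parameter step could appear there, but SAP 1.5 already prints the selection rule without one.

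A reader might go further and infer that an undated visit always beats a dated one and that dated visits should therefore take precedence. The first part fails on the target day. The second is a trade-off: the undated page carries its window label, while a dated visit in the Month 18 window can lie up to 639 − 548 = 91 days from the target.

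**Conclusion.** The point holds as a limited weakness in the written rule. SAP 1.5 selects by distance, then by earlier date, then by record order, and at no step by whether the parameter is present. Given Protocol 3.2.2 and 3.3.6, a measured value can be replaced by a blank in any by-window or change-from-baseline efficacy table and in table 2.1.4.

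The size is unknown. The 1 to 8% relative gain rests on assumed d and q, two visits per shared window and independent recording. Positive correlation lowers it, to zero at the extreme.

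A reader might infer that data are lost in every follow-up table. The documents show only that they can be, because they give neither the number of shared windows nor the pattern of blanks. Nor do they support reading the average number of records per patient as evidence of crowded windows. The preference for undated visits is near-total under the rule, but its effect cannot be judged without a count of such visits.

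**What to change.** In SAP 1.5, replace selection of the visit by selection of the value:

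- For each parameter and window, keep the non-missing value closest to the target day, with the existing tie rules.
- Take DAS28 as the value recorded at a single visit, and do not assemble it from components measured at different visits.
- State the target days as day numbers.
- Report, by window, how many patients had more than one visit and how many had an undated visit.
- For undated visits, rely on that count or add a sensitivity analysis without them. Do not impose a fixed precedence for dated visits.

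The cost is a few sentences in the SAP, a small program change and one short table. The downside is that different parameters in the same window may come from different visits, which a footnote to the tables should say.
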